7.4.5 Practical Measures to Minimise Bias

Interim analysis

Outputs featuring unblinded treatment assignments will be created by the unblinded analysis team within [REDACTED] and shared with the unblinded personnel at [REDACTED] (Interactive Response Technology Vendor) who will implement the required changes to the randomisation schedule in their system.. Unblinded results will not be shared with any study site staff, participants, or any members of the study team who will be involved in the collection, review or analysis of individual study data.

The members of the unblinded team will not be involved in any aspects of study conduct, including in the development of the final summaries and analyses for the study. No data which may have the potential to unblind will be released beyond the unblinded personnel.

Cohorts 1-3 analysis

Cohorts 1-3 data will be unblinded to the [REDACTED] study team and the sponsor after the cohorts 1-3 DBL. Cohort 4 data will remain blinded till the end of study.

7.4.6 Documentation of Interim Analyses

Interim analysis

All unblinded data and summaries, together with any meeting minutes in which unblinded data is discussed will be held in a restricted file structure by the unblinded statistician until after the study has finished and the data has been unblinded after DBL.

Cohorts 1-3 analysis

Unblinded summaries will be shared with the sponsor as cohorts 1-3 data will be unblinded after the cohorts 1-3 DBL.

7.5 Multi-centre Studies

Results will be presented for all centres combined. For the inferential analyses the effect of region will be assessed for significance in the models.

7.6 Multiple Testing

The focus of this study is on model estimation of treatment effects and as such no adjustments will be made for multiple testing in this study.

7.7 Visit Windows

All data will be reported according to nominal visits. For example, if a Week 2 visit occurred on Day 16 instead of the nominally expected Day 14 it will be reported and included in the summary statistics/statistical analyses for Week 2.

Scheduled visits which occur outside the protocol-specified visit window (e.g., if the Week 2 visit occurred on Day 19 outside of the Day 12-18 window), this will be noted as a protocol deviation but data collected will still be included in all summary and analysis tables.

Unscheduled visits and Early Termination visit will not be included in summary or analysis tables, unless they are baseline measurements, provide data towards a safety endpoint which looks at worst-case post-baseline, or if a visit is a rescue therapy unscheduled visit.

Week 20 visit will be included in the summaries, but no analysis will be done at this visit.

For the rescue therapy, subjects who started rescue therapy outside of a scheduled visit should complete assessments required for the rescue therapy unscheduled visit. This data will only be included in tables and figures in cases where the last off-rescue observation carried forward imputation method is used to account for the intercurrent event of rescue therapy.

All listings will include all collected data even if they are from an unscheduled visit.

8 Summary of Study Data

All continuous variables will be summarized using the following descriptive statistics: n (non-missing sample size), mean, SD, median, maximum and minimum. The frequency and percentages (based on the non-missing sample size) of observed levels will be reported for all categorical measures.

In general, all data will be listed, sorted by cohort (1, 2, and 3 for the cohorts 1-3 analysis and 1-4 for the final analysis), randomised treatment (Placebo, EDP1815), site number and participant number. Relevant listings will include whether the assessment was performed and the date, study day/visit and time of the assessment as applicable.

Unless otherwise specified below, all summary tables will be structured with a column for each treatment. Where appropriate, columns combining all placebo participants, all EDP1815 participants and an overall total column may also be presented.

For summaries of study disposition, demographic and baseline data and study treatment compliance, columns will be ordered and labelled as follows:

- Cohort 1 Placebo
- Cohort 1 EDP1815
- Cohort 2 Placebo
- Cohort 2 EDP1815
- Cohort 3 Placebo
- Cohort 3 EDP1815
- Cohort 4 Placebo (final analysis only)
- Cohort 4 EDP1815 (final analysis only)
- All Placebo
- All EDP1815
- Total

For cohorts 1-3 efficacy outputs, columns will be ordered and labelled as follows:

- All Placebo
- Cohort 1 EDP1815
- Cohort 2 EDP1815
- Cohort 3 EDP1815
- Cohorts 2+3 EDP1815
- All EDP1815

For cohort 4 efficacy outputs, columns will be ordered and labelled as follows:

- Cohort 4 Placebo
- Cohort 4 Matched Placebo
- Cohort 4 EDP1815
- Cohort 1 EDP1815

For concomitant medication and safety outputs, columns will be ordered and labelled as follows:

- All Placebo
- Cohort 1 EDP1815
- Cohort 2 EDP1815
- Cohort 3 EDP1815
- Cohort 4 EDP1815 (final analysis only)
- All EDP1815

For the analysis:

- For study disposition summaries where it is appropriate to report information on participants who failed screening, the enrolled population will be used.
- For safety summaries, where data is assigned to specific scheduled visits, the safety population with SDPS1 will be used.
- For safety summaries, where all other safety data is presented (including adverse events and worst-case change from baseline endpoints), the safety population with SDPS2 will be used.
- For the primary estimand and all secondary and exploratory estimands, full analysis population with EDPS1 will be used.
- For the supplementary estimands for the primary endpoint, full analysis population with EDPS2-EDPS5 will be used.
- Selected secondary response endpoints will also have secondary supplementary estimands: full analysis population with EDPS2 and EDPS6 will be used for endpoints based on EASI, vIGA and PP-NRS.
- For the secondary count endpoints, full analysis population with EDPS7 will be used.
- For the exploratory endpoints, full analysis population with EDPS1 will be used.
- For all other summaries and analyses the full analysis population will be used.

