The severity and frequency of Adverse Events will be used to evaluate the safety and tolerability of EDP1815.

Exploratory endpoints: A number of exploratory endpoints will be evaluated to determine further aspects of treatment efficacy including time to achieve clinical response and patient reported health outcomes. Changes in eosinophils, immune protein markers and immune cell RNA profile will be used to evaluate the effect of EDP1815 treatment on biomarkers in blood. A fecal sample will be used for microbiome profiling. Human Leukocyte Antigen (HLA) typing will be performed in those participants who consent to assess the correlation with clinical outcomes.

Brief Study Design: This study will evaluate EDP1815 in participants with mild, moderate, and severe atopic dermatitis, to compare efficacy, safety, and tolerability to placebo. The Investigational Medicinal Product (IMP) is EDP1815 or matching placebo. The study will be blinded to the participants, Investigator, and Sponsor.

Approximately 405 participants will be randomized to receive either EDP1815 or placebo (295 to EDP1815: 110 to placebo) and treated for 16 weeks. Following end-of-treatment assessments, participants may enter a 4-week post-treatment follow-up period or may elect to participate in an Open Label Extension (OLE) Protocol for EDP1815, if available. Cohorts 1, 2 & 3 will be run concurrently, and Cohort 4 recruitment will commence after enrollment for Cohorts 1, 2, & 3 are completed.

Participants will be dosed with EDP1815 or matching placebo administered as the following:

- **Cohort 1:** 1.6×10^{11} total cells of EDP1815 or matching placebo administered as 2 capsules once daily.
- **Cohort 2:** 6.4×10^{11} total cells of EDP1815 or matching placebo administered as 2 capsules once daily.
- **Cohort 3:** 6.4×10^{11} total cells of EDP1815 or matching placebo administered as 1 capsule of 3.2×10^{11} cells twice daily.
- **Cohort 4:** 8.0×10^{10} total cells of EDP1815 or matching placebo administered as 1 capsule once daily.

Participants in Cohorts 1, 2, & 3 will be randomized in a 3:1 ratio (225 to EDP1815: 75 to placebo). Participants in Cohort 4 will be randomized in a 2:1 ratio (70 to EDP1815: 35 to placebo). Randomization to Cohort 4 will not start before randomization to Cohorts 1, 2 & 3 have completed.

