4. STUDY DESIGN

4.1. Study Description

This is a randomized, double-blind, placebo-controlled study to evaluate the efficacy, safety and tolerability of EDP1815 as compared to placebo in participants with mild, moderate and severe atopic dermatitis.

This study will consist of 4 cohorts with a possible interim analysis prior to end of recruitment in Cohorts 1, 2 & 3. The purpose of this interim analysis is to check the assumptions around placebo response rate.

Approximately 100 participants will be randomly allocated to each of Cohorts 1, 2, & 3. These cohorts will run concurrently. Within each cohort, participants will then be randomized to treatment in a 3:1 ratio (75 to EDP1815, 25 to placebo). Therefore, across Cohorts 1, 2, & 3, approximately 225 participants will be randomly assigned to receive EDP1815, and 75 participants will be randomized to matching placebo for 16 weeks. Following end-of-treatment assessments, participants may enter a 4-week post-treatment follow-up period or may elect to participate in an Open Label Extension (OLE) protocol for EDP1815, if available.

- **Cohort 1:** 1.6×10^{11} total cells of EDP1815 or matching placebo administered as 2 capsules once daily.
- **Cohort 2:** 6.4×10^{11} total cells of EDP1815 or matching placebo administered as 2 capsules once daily.
- **Cohort 3:** 6.4×10^{11} total cells of EDP1815 or matching placebo administered as 1 capsule of 3.2×10^{11} cells twice daily.

Cohort 4 will run after enrollment is completed in Cohorts 1, 2, & 3. Approximately 105 participants in this cohort will be randomized to treatment in a 2:1 ratio (70 to EDP1815, 35 to placebo). Participants will be treated for 16 weeks. Following end-of-treatment assessments, participants may enter a 4-week post-treatment follow-up period or may elect to participate in an Open Label Extension (OLE) protocol for EDP1815, if available.

- **Cohort 4:** 8.0×10^{10} total cells of EDP1815 or matching placebo administered as 1 capsule once daily.

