6. STUDY TREATMENT(S)

6.1. Investigational Medicinal Product(s)

Investigational Medicinal Product (IMP) is defined as any investigational treatment(s), marketed product(s), placebo, or medical device(s) intended to be administered to a study participant according to the study protocol.

All IMP in this study will be administered orally. EDP1815 will be supplied as capsules that are enteric-coated to release the contents upon gastric emptying. EDP1815 enteric-coated capsules contain lyophilized *Prevotella histicola*, mannitol, magnesium stearate, colloidal silicon dioxide, hydroxypropyl methylcellulose, methacrylic acid-ethyl acrylate copolymer, talc, triethyl citrate, titanium dioxide, and iron oxide.

EDP1815 capsules will be manufactured in the following dose strengths and associated enteric coating thickness (EC). The thickness of the capsule enteric coating for Cohort 4 is thinner (EC2) than the capsule enteric coating for Cohorts 1, 2, & 3 (EC1):

- Cohort 1: 8.0×10^{10} total cells per capsule (EC1)
- Cohort 2 & 3: 3.2×10^{11} total cells per capsule (EC1)
- Cohort 4: 8.0×10^{10} total cells per capsule (EC2)

The drug substance used in Cohorts 1 and the 4 is manufactured by a different process than used in Cohorts 2 and 3. The drug substance in Cohorts 2 and 3 was manufactured using an optimized process to yield a higher concentration of microbe per capsule. It has been demonstrated to be similar to the drug substance in DTH mouse and healthy-volunteer human models. All IMP, regardless of manufacturing processes, is identical in appearance. Further information is detailed in the EDP1815 IB. The drug product is manufactured by [REDACTED].

The matching placebo is identical in appearance but does not contain *P histicola* or any other bacteria. The coated placebo capsules are composed of microcrystalline cellulose, magnesium stearate, hydroxypropyl methylcellulose, methacrylic acid-ethyl acrylate copolymer, talc, triethyl citrate, titanium dioxide, and iron oxide. The matching placebo capsules are manufactured by [REDACTED].

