The analyses for Cohort 4 will compare EDP1815 8.0x10¹⁰ to a combined control group including the Cohort 4 placebo participants (approximately 35) and set of matched placebo participants from Cohorts 1-3 (approximately 35). This will provide a total of approximately 70 placebo participants, resulting in a 1:1 comparison between EDP1815 8.0x10¹⁰ and placebo. This combined placebo cohort will be referred to as the Cohort 4 Matched Placebo group.

While not enrolled concurrently to Cohort 4, the Cohort 1-3 placebo group provides an appropriate population to supplement the Cohort 4 placebo group, increasing the power of the comparison of EDP1815 8.0x10¹⁰ to placebo and precision of the treatment effect estimates (Viele, 2014). A propensity-score based matching algorithm will be used to select patients from the Cohort 1-3 Placebo group in to order balance key baseline characteristics (Austin, 2011). Matching will be performed based on propensity scores derived from baseline characteristics such as IGA, EASI score, BSA, gender, and country. Full details of the matching algorithm are provided in the SAP.

Summary tables for Cohort 4 will include a column for the Cohort 4 Only Placebo group in addition to columns for the Cohort 4 Matched Placebo group as well as the EDP1815 8.0x10¹⁰ group.

Analysis tables and figures will include only the Cohort 4 Matched Placebo group and the EDP1815 8.0x10¹⁰ group and all primary and secondary comparisons will be between these two groups.

As an exploratory analysis, analyses may be repeated including the EDP1815 1.6x10¹¹ QD (Cohort 1) treatment group in the statistical models for Cohort 4. For these analyses the comparison of interest will be between the two active EDP1815 treatment groups (Cohort 1 vs Cohort 4).

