4.5 Exploratory Efficacy Analyses

The exploratory efficacy analyses described in the main SAP will also be produced for cohort 4.

5 Technical Details

In addition to the technical details of processes described in the main SAP where [REDACTED] team is involved, the Bayesian dynamic borrowing sensitivity analysis of the primary endpoint will be conducted by [REDACTED] utilizing RBest package in R.

6 Summary of Changes from the Protocol

The SAP Addendum is based on the latest Protocol v5.0.

Table 1: Summary of Changes from the Protocol and the main SAP

Protocol Version	Summary of Change	Justification for change
V5.0	Protocol states the sensitivity analysis for the primary endpoint of Cohort 4 will utilize a commensurate prior method to perform dynamic borrowing. The approach has been updated to utilize robust mixture priors to perform the dynamic borrowing sensitivity analysis	The robust mixture priors method is more robust due to the inclusion of a weakly informative component in the prior distribution
V5.0	Sensitivity analysis to compare cohort 4 EDP1815 to a cohort 4 placebo was added.	Due to the concerns in cohorts 1-3 placebo participants similarity to cohort 4 placebo, it was decided to add sensitivity analysis (within cohort 4 comparison). So in the case of different behaviour of cohort 4 placebo participants, sensitivity analysis vs. cohort 4 placebo still will be valid, however, with less power (as described in the Protocol).

7 Bibliography

- Austin, Peter C. 2011. *Optimal caliper widths for propensity-score matching when estimating differences in means and differences in proportions in observational studies*. Pharm Stat. 2011 Mar; 10(2): 150–161. doi:10.1002/pst.433.
- Beat Neuenschwander, Sebastian Weber, Heinz Schmidli, Anthony O'Hagan. 2020. *Predictively consistent prior effective sample sizes*. doi: <https://doi.org/10.1111/biom.13252>.
- Heinz Schmidli, Sandro Gsteiger, Satrajit Roychoudhury, Anthony O'Hagan, David Spiegelhalter, Beat Neuenschwander. 2014. *Robust meta-analytic-predictive priors in clinical trials with historical control information*. doi: <https://doi.org/10.1111/biom.12242>.

8 Appendix 1: List of Tables, Figures and Listings

Only additional outputs not listed in the main SAP included in this section.

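### No planned final safety table sets Cohort 4 EDP1815 beside its own concurrently randomised placebo group

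*SAP*

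**What the plan says.** SAP section 8 (Summary of Study Data) sets the table columns by type of output. The safety list is introduced with "For concomitant medication and safety outputs, columns will be ordered and labelled as follows" and has six entries: All Placebo, Cohort 1 EDP1815, Cohort 2 EDP1815, Cohort 3 EDP1815, Cohort 4 EDP1815 (final analysis only) and All EDP1815. The same section gives a Cohort 4 Placebo column to the disposition, baseline and compliance tables and to the Cohort 4 efficacy outputs.

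Protocol 11.2 plans two sets of tables, figures and listings, one for Cohorts 1-3 and one for Cohort 4. In its Cohort 4 text it adds: "Summary tables for Cohort 4 will include a column for the Cohort 4 Only Placebo group". Protocol 11.4.6 says that safety data are summarised by treatment group.

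On timing, Protocol 4.1 says: "Cohort 4 will run after enrollment is completed in Cohorts 1, 2, & 3".

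SAP 7.4.3 runs every planned analysis on Cohorts 1-3 alone once those cohorts are locked. SAP 9.1 uses the label 'all placebo' for the pooled Cohorts 1-3 placebo group in efficacy. SAP section 3 describes the Addendum as covering Cohort 4 efficacy, and the tables listed in the Addendum are efficacy tables. Neither SAP section 13 nor the Addendum's change table (its section 6) mentions the safety column layout.

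**The concern.** Randomisation protects a comparison only among people who could have been allocated to either arm at the same time. For Cohort 4 EDP1815 that means the 35 Cohort 4 placebo participants. The Cohorts 1-3 placebo participants were randomised earlier, at 3:1 rather than 2:1, and cohort membership is not blinded (Protocol 6.10). Two of those three cohorts took two capsules once daily and the third took one capsule twice daily, against one capsule once daily in Cohort 4, whose capsules also have a thinner enteric coating (Protocol 6.1 and Table 6-1). Background adverse-event reporting can change with calendar time and with such conditions.

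The sponsor already treats comparability as open for efficacy. The Addendum's change table adds a within-Cohort 4 comparison "Due to the concerns in cohorts 1-3 placebo participants similarity to cohort 4 placebo". Nothing equivalent is planned for safety.

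What is at stake is the safety reading of the Cohort 4 regimen. The rationale in the protocol's amendment section gives one capsule once daily as the anticipated Phase 3 regimen. A period difference could look like a drug effect in that column, or could hide one.

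**Working it through.** **Inputs.** Planned allocation from the Protocol Summary and Protocol 4.1: 75 EDP1815 and 25 placebo in each of Cohorts 1, 2 and 3; 70 EDP1815 and 35 placebo in Cohort 4.

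**Reproducing the plan's totals.** EDP1815: 3 × 75 + 70 = 295. Placebo: 3 × 25 + 35 = 110. Total: 295 + 110 = 405. All three match the Protocol Summary.

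**Make-up of All Placebo, if it pools four cohorts.** Randomised before Cohort 4 opened: 75/110 = 68.2%. Concurrent with Cohort 4: 35/110 = 31.8%.

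**What a period shift does.** Let p13 and p4 be the background event rates in the two periods, with d = p4 − p13 and no drug effect.

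- All Placebo rate = (75·p13 + 35·p4)/110.
- Cohort 4 EDP1815 minus All Placebo = p4 − (75·p13 + 35·p4)/110 = (75/110)·d = 0.68d.
- EDP1815 in any of Cohorts 1-3 minus All Placebo = −(35/110)·d = −0.32d, in the final tables only. In the Cohorts 1-3 run under SAP 7.4.3, All Placebo is their own 75 participants and the term is 0.
- All EDP1815 minus All Placebo = (70/295 − 35/110)·d = (0.237 − 0.318)·d = −0.08d, which is small.

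**If All Placebo instead means Cohorts 1-3.** The Cohort 4 term becomes the whole of d, the Cohorts 1-3 term is 0, and the Cohort 4 placebo participants appear in no safety table.

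**Illustrations, four-cohort pooling.** The rates are assumed.

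| Cohorts 1-3 placebo | Cohort 4 placebo | Cohort 4 EDP1815 | All Placebo | True difference | Difference as read |
|---|---|---|---|---|---|
| 30% | 35% | 35% | 31.6% | 0 | +3.4 points |
| 30% | 40% | 40% | 33.2% | 0 | +6.8 points |
| 30% | 45% | 45% | 34.8% | 0 | +10.2 points |
| 40% | 30% | 30% | 36.8% | 0 | −6.8 points |
| 45% | 30% | 40% | 40.2% | +10 points | −0.2 points |

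The last row shows masking: (75 × 45 + 35 × 30)/110 = 40.2%, so a real 10-point excess disappears.

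**Price of the concurrent column.** At an assumed 30% rate in both groups, the 95% half-width of a difference is 1.96·√[0.3 × 0.7 × (1/70 + 1/n)]. With n = 35 this is 18.6 points; with n = 110 it is 13.7 points.

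**The case against.** The strongest reply is that little is lost.

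- **Safety is descriptive.** Protocol Table 11-4 asks for summary statistics or incidence in each treatment group, with no planned difference, interval or p-value. This stands. The 0.68d describes how a reader compares two columns, not an error in a planned estimate.
- **Cohorts 1-3 get undiluted safety tables.** SAP 7.4.3 provides them. This also stands, with one limit: SAP 7.4.1 commits only the Cohorts 1-3 efficacy tables and listings to the study report.
- **Some concurrent information exists.** Listings are sorted by cohort and treatment. Disposition tables show discontinuation reasons with a Cohort 4 Placebo column. The Cohort 4 versions of the rescue-therapy and antimicrobial-use outputs are efficacy outputs and carry that column too. Participant counts could be recovered by subtracting the Cohorts 1-3 run from the final one, if the data do not change after the first lock. None of this is an adverse-event, laboratory, ECG or vital-sign table showing the concurrent comparison.
- **The periods may overlap.** Cohort 4 follows the end of enrolment in Cohorts 1-3, not the end of follow-up, so calendar overlap is possible. The 68% refers to time of randomisation.

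A reader might infer that the SAP breaks an explicit protocol promise of a Cohort 4 placebo column in the safety tables. The documents do not go that far. The sentence in Protocol 11.2 is not limited to efficacy, but it sits among text on matching and power and pairs the column with a Matched Placebo column that nobody would expect in safety tables. A reader might also take the Addendum's remark as an admission that the placebo groups differ on safety. It justifies an efficacy sensitivity analysis and gives no calendar-time or safety reason.

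**Conclusion.** The gap is real and modest. As written, Cohort 4 EDP1815 is shown in the final safety and concomitant-medication tables beside a placebo column that is 68% non-concurrent by randomisation (100% on the SAP 9.1 meaning), and its own 35 placebo participants are not shown separately. Safety and concomitant medication are the exception within SAP section 8. The layout also departs, without a record in SAP section 13, from the separate Cohort 4 table set in Protocol 11.2. That section does record another change to safety outputs, so such changes were within its scope.

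The shares rest on planned numbers. The 0.68d rests on four-cohort pooling and no drug effect. The size of d is unknown: the documents give no adverse-event rates, and every rate used above is an assumption. The documents do not show that a shift occurred, and they do not support a claim that Cohorts 1-3 are compared throughout with a diluted placebo group. That dilution (−0.32d) is confined to the final tables.

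**What to change.** In SAP section 8, for the safety and concomitant-medication outputs:

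1. Add the columns Cohorts 1-3 Placebo and Cohort 4 Placebo (final analysis only).
2. Keep All Placebo beside them and define it for these outputs as all four cohorts, since SAP 9.1 uses the same label for Cohorts 1-3.
3. State that Cohort 4 EDP1815 is read first against Cohort 4 Placebo, and EDP1815 in Cohorts 1-3 against Cohorts 1-3 Placebo, with All Placebo as the larger reference for uncommon events.
4. Record the layout in SAP section 13, with a sentence on how it meets the two-set plan in Protocol 11.2.

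The cost is SAP wording, two more columns and the matching programming. No new data are needed. The drawback is the imprecision of a 35-participant column, which is why All Placebo should stay.
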